12.10.11. Pharmacodynamic and/or Biomarker Tables

Pharmacodynamic and Biomarker: Tables					
No.	Population	IDSL / Example Shell	Title	Programming Notes	Deliverable [Priority]
Exploratory Biomarkers					
6.1.	Safety	PD_T1	Summary Statistics for Actual and Percentage Change from Baseline in Biopsy Tissue Inflammatory Biomarkers (Parts A and B)	One page for each cell type/measure by visit/time and treatment	SAC [1]
6.2.	Safety	PD_T2	Adjusted Mean (95% CI) of Percentage Change from Baseline in Biopsy Tissue Inflammatory Biomarkers (Parts A and B)	One page for each cell type/measure by visit/time and treatment/dosing regimen	SAC [1]
Pathway and Target Engagement					
6.3.	Safety	EFF_T1	Summary Statistics for Observed TEAR1 % Target Engagement (Parts A and B)	Separate summaries for sample type (Blood/Biopsy) % Target Engagement by visit/time	SAC [1]
6.4.			Summary Statistics for Predicted TEAR1 % Target Engagement based on predicted GSK2982772 trough concentrations (Parts A and B)		
6.5.	Safety	PD_T3	Adjusted Mean (95% CI) of TEAR1 % Target Engagement in Blood (Parts A and B) by Randomised Treatment		SAC [1]
6.6.	Safety	PD_T3	Adjusted Mean (95% CI) of TEAR1 % Target Engagement in Biopsy Tissue (Parts A and B) by Randomised Treatment		SAC [1]
6.7.	Safety	EFF_T1	Summary Statistics of Pathway Engagement (Parts A and B) by Randomised Treatment	Separate summaries for sample type (Blood/Biopsy)	SAC [1]
6.8.	Safety	PD_T3	Adjusted Mean (95% CI) of Pathway Engagement in Blood (Parts A and B) by Randomised Treatment		SAC [1]
6.9.	Safety	PD_T3	Adjusted Mean (95% CI) of Pathway Engagement in Biopsy Tissue (Parts A and B) by Randomised Treatment		SAC [1]

Pharmacodynamic and Biomarker: Tables					
No.	Population	IDSL / Example Shell	Title	Programming Notes	Deliverable [Priority]
mRNA Expression					
6.10.	Safety	PD_T4	Summary of mRNA Expression of Inflammatory Gene Transcripts (Parts A and B) by Randomised Treatment	Separate summaries for sample type (Blood/Biopsy) qPCR – micarray dataset	SAC2 [1]
6.11.	Safety	PD_T5	Frequency Table Summarising the Number of Probe Sets with Various Fold Change (Parts A and B) by Randomised Treatment	Separate summaries for sample type (Blood/Biopsy). Use cut-offs 1.5 and -1.5 initially. Change to -1.25 and 1.5 if no one achieves the initial cut-offs	SAC2 [1]
6.12.	Safety	PD_T6	Summary of Adjusted Mean Fold Changes in mRNA Expression of Inflammatory Gene Transcripts (Parts A and B) by Randomised Treatment	Separate summaries for sample type (Blood/Biopsy). If Adj Mean FC lies between -1 and 1 then do not include on table	SAC2 [1]
6.13.	Safety		Summary of Analysis for Microarray mRNA Intensity Data in Blood	GSK to produce Only to be produced for significant probsets based on adjusted p-values. If Adj Mean FC lies between -1 and 1 then do not include on table	SAC2 [1]
6.14.	Safety		Summary of mRNA Percentage Inhibition of Inflammatory Gene Transcripts in Blood	GSK to produce Only to be produced for significant probsets based on adjusted p-values.	SAC2 [1]

Pharmacodynamic and Biomarker: Tables					
No.	Population	IDSL / Example Shell	Title	Programming Notes	Deliverable [Priority]
6.15.	Safety		Summary of Analysis for Microarray mRNA Percentage Inhibition Data in Blood	GSK to produce Only to be produced for significant probsets based on adjusted p-values. If Adj Mean FC lies between -1 and 1 then do not include on table	SAC2 [1]

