- To identify the most robustly expressed probesets, the data can be filtered to remove low intensity probesets, low quality and control probe sets prior to analysis. This could be done simply by excluding all probesets where all observations are <6 (on the \log_2 scale). Note it has been observed empirically that when you get below 100 (6.6 on the \log_2 scale) you are into the noise of the assay. Other more stringent methods of filtering the data could be used. In total, there are 53,617 probesets that could be analysed.
- To compare the expression value for each probeset, the following linear repeated measures mixed effects model will be fitted to each probeset that passes any pre-filtering, with \log_2 (intensity) as the response variable. Randomised Treatment by visit, randomised treatment and visit will be fitted as fixed effects and participant as a random effect. Example SAS code is given below:

```
proc mixed data=data;
ods output covparms=cov lsmeans=lse estimates=Compare;
class subjid treatment visit;
model lgintensity= treatment visit treatment*visit /ddfm=kr;
repeated visit / subject=subjid type=un;
lsmeans treatment*visit / diff cl alpha=0.05;
run;
```

- For each probeset analysed adjusted means with corresponding 95% CI and fold changes with corresponding 95% CI's can be outputted. The fold change is derived from the ratio of the back-transformed estimate of the difference between adjusted means.

Transcriptomics - MicroArray RNA Analysis

- Where appropriate, particularly with microarray data, multiple testing will be considered using the Benjamini-Hochberg correction (*Benjamini, Y; J Royal Stat Soc 1995;57:289-300*) to calculate FDR adjusted p-values. Proc Multtest incorporating the FDR adjusted p-value option in SAS is used to convert the raw p-values from the proc mixed code above into the FDR adjusted p-values based on the Benjamini-Hochberg correction. Example code to generate the FDR adjusted p-values is given below:

```
data pvalues (keep = probsid label probt rename=(probt=raw_p));
    set compare;
run;

proc multtest pdata=pvalues fdr out=FDRres noprint;
run;
```

- Where the FDRes dataset will include the following columns:

p-values		
Test	Raw	False Discovery Rate
1	0.2828	0.9243
2	0.9437	0.9437
3	0.0350	0.6305
etc.		

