- Appropriate outputs will be created containing all the results for the relevant comparisons for all analysed probesets. A summary may be generated, including probeset ID, gene ID, time point, adjusted means with corresponding 95% CI for each randomised treatment group, Benjamini-Hochberg FDR adjusted p-value and fold changes corresponding 95% CI from each comparison. Note that probeset ID is required if there is more than one probeset per gene.
- For each comparison subsets of probesets will be identified based on an appropriate fold-change, for example, fold changes >1.5 or <-1.5. The proportion of probesets with fold changes >1.5 or <-1.5 will be summarised in a frequency table.
- The outputs should be reviewed by the study team and the pre-agreed subset of biologically relevant probesets will be reported within the CSR. If based on the fold-changes observed other probesets, which were not pre-specified in the RAP, are deemed relevant then these should be interpreted with caution.
- Exploratory graphical reporting on the back-transformed scale can include:
 - Log₂ (intensity) plotted against time point separately for individual participants, grouped by randomised treatment group
 - Adjusted mean intensity and 95 CI% plotted by randomised treatment group and time point.

Transcriptomics – Microarray Percentage Inhibition Analysis

- The \log_2 normalised data is back transformed and the percentage inhibition is derived on a participant level on the back transformed data for each probeset. The percentage inhibition will be determined for each probeset per participant, where it is defined as the reduction from baseline. For example:

Day X – baseline = -40% would be a 40% reduction (i.e. -40% change from baseline) which in turn is defined as a 40% inhibition. So, the percentage inhibition would be calculated as:

$$[(\text{Day } x - \text{Baseline}) / \text{Baseline}] * -100 = \% \text{ inhibition}$$

- A subset of probesets may be identified and individual participant mRNA intensities and percentage inhibitions may be listed, summarised and plotted appropriately for each selected probeset. The selected probesets will be statistically analysed appropriately, and the output from the mixed effects model summarised. The probeset, gene or gene description will be included in the outputs.

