- To compare the percentage inhibition for each selected probeset, the following linear repeated measures mixed effects model will be fitted to each selected probeset, with percentage inhibition as the response variable. Randomised Treatment by visit, randomised treatment and visit will be fitted as fixed effects and participant as a random effect. Example SAS code is given below:

```
proc mixed data=data;
class subjid treatment visit;
model perinhibit= treatment visit treatment*visit /ddfm=kr;
repeated visit / subject=subjid type=un;
lsmeans treatment*visit / diff cl alpha=0.05;
run;
```

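### The percentage-inhibition tables show only probesets that pass an FDR cut on the same data, so a pre-agreed probeset that misses the cut has no inhibition result and modest effects that pass are overstated

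*SAP*

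**What the plan says.** Section 10.1.3.1 sets out two analyses of the microarray data.

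- **Intensity.** A repeated-measures model is fitted to log2 intensity for each probeset that passes filtering, up to 53,617 in all. The Benjamini-Hochberg correction is applied to its raw p-values "to calculate FDR adjusted p-values". No numerical cut-off is given. The study team reviews the outputs, and "the pre-agreed subset of biologically relevant probesets will be reported within the CSR".
- **Percentage inhibition.** Reduction from baseline is derived per participant and probeset. Then "A subset of probesets may be identified", with no rule for choosing it. "To compare the percentage inhibition for each selected probeset, the following linear repeated measures mixed effects model will be fitted to each selected probeset", with the interval statement "lsmeans treatment*visit / diff cl alpha=0.05".

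The display list in 12.10.11 supplies the missing rule. Table 6.13 (intensity analysis), Table 6.14 (descriptive inhibition summary) and Table 6.15 ("Summary of Analysis for Microarray mRNA Percentage Inhibition Data in Blood") all carry the note "Only to be produced for significant probsets based on adjusted p-values".

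**The concern.** The rule has two consequences. First, the methods section promises results for genes named in advance, while the table note removes those that are not significant. A programmer who follows the note produces an inhibition display made up only of hits.

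Second, the inhibition estimates come from the same participants whose intensities decided which probesets are shown, and their 95% intervals take no account of that selection. Where true effects are modest, the probesets that pass are those whose estimates happened to be large. At stake is how a reader judges the size of pathway inhibition in blood, and whether the absence of inhibition in a pre-agreed gene is visible.

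**Working it through.** **1. Which displays show inhibition.**

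| Display | Content | FDR filter |
|---|---|---|
| Table 6.10, Figures 6.17-6.19, Listing 76 | Expression, intensity or fold change | None |
| Table 6.13 | Intensity analysis, blood | Yes |
| Table 6.14 | Inhibition, descriptive, blood | Yes |
| Table 6.15 | Inhibition, model, blood | Yes |

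No unfiltered display shows percentage inhibition. The gap for pre-agreed probesets follows from the text and needs no simulation.

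**2. Size of the distortion.** The SAP gives no error rate or power for this analysis, so there is no figure to reproduce.

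Inputs from the SAP: 53,617 probesets (10.1.3.1); about 36 participants randomised 2:1 (2.3), hence 24 v 12; inhibition = -100 x (visit - baseline)/baseline.

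Assumed: SD 0.5 log2 units; baseline-visit correlation r of 0.3 to 0.7; independent probesets; 0.5-2% of them truly lower on active treatment; one post-baseline visit; Benjamini-Hochberg at 5%. Selection is on the between-arm difference at the visit, the nearest reading of the SAP's model code. Inhibition is then compared by a two-sample t-test with an ordinary 95% interval.

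The true between-arm inhibition for an f-fold reduction is 100 x (1 - 1/f) x exp(v/2), with v = 2 x 0.5^2 x (1 - r) x (ln 2)^2. For f = 1.5:
- r = 0.3: v = 0.168, so 33.3 x 1.088 = 36.3 points.
- r = 0.7: v = 0.072, so 33.3 x 1.037 = 34.6 points.

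Simulated results at a true 1.5-fold reduction, over these ranges:
- About 7-27% of such probesets pass the cut.
- Mean estimate among those that pass is about 38-47 points, against 35-36.
- Interval coverage among selected probesets is 0.83-0.88, against 0.89-0.93 without selection.

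Effect of true size at r = 0.5 with 1% of probesets changed (fold = 2^(0.5 x effect in SD)); estimates and coverage are for truly changed probesets:

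| True effect | Pass the cut | Mean estimate v true | Coverage, selected v unselected |
|---|---|---|---|
| 1 SD (1.41-fold) | 4% | 43.1 v 31.1 | 0.81 v 0.91 |
| 1.5 SD (1.68-fold) | 59% | 46.9 v 43.0 | 0.91 v 0.90 |
| 2 SD (2-fold) | 96% | 54.1 v 53.1 | 0.90 v 0.89 |

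The SAP does not fully fix the contrast used for selection. If it were the difference in change from baseline, the 1 SD row would become 53.3 v 31.1 with coverage 0.34 v 0.92. At 2-fold the bias would be 0.3 to 4.2 points over r = 0.7 to 0.3.

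**3. The second p-value.** Among unchanged probesets that passed the cut on the visit difference, 25-62% also had p < 0.05 in the inhibition model, against a nominal 5%. The settings with small effects rest on very few such probesets. Both models use the same visit intensities, so agreement between them is expected.

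**The case against.** Several points on the other side stand.

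- The methods text does not say that the inhibition model is fitted only to significant probesets. It leaves the subset open, and the note governs which tables are produced. That the adjusted p-values behind Table 6.15 come from the intensity model is an inference, though no others are defined.
- The promise about pre-agreed probesets sits in the intensity block and does not mention inhibition. The same block also calls for outputs with results for all analysed probesets. A reader might infer that non-significant genes vanish from the report. They do not: their expression remains in Table 6.10, Figures 6.17-6.19 and the listings.
- A reader might also measure undercoverage against 95% and blame selection for all of it. Unselected coverage is already 0.89-0.93 at 1.5-fold, because percentage change is skewed.
- Unchanged probesets are a small part of the selected set: 16.0 of 332.2 per run (4.8%) in the 1.5 SD setting above. The inflated second test therefore touches few rows, and the SAP never calls the inhibition result confirmation.
- The work is exploratory, and Section 5.5 disclaims multiplicity adjustment apart from the FDR process.

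These points limit the reach of the concern. They do not explain why a gene named in advance should lose its inhibition result for missing the cut.

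**Conclusion.** The point holds as a narrow reporting issue and a cheap improvement to consider. The table note and the reporting promise have not been reconciled, and following the note gives an inhibition display of significant probesets only. Among those, modest effects are overstated: roughly 3 to 11 points at a true 1.5-fold reduction, taking 38 against 35 and 47 against 36. Selection costs about five points of coverage there. With selection on the visit difference, 2-fold effects are overstated by about 1 point or less and coverage is not reduced.

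These sizes rest on the assumed SD, correlation, share of changed probesets, independence and 5% cut, none of which the SAP states. The stronger reading, that the inhibition analysis is wholly circular and invalid, is not supported: the distortion depends on effect size, Table 6.14 contains no test, and Table 6.13 is an ordinary FDR hit list. No primary or secondary conclusion is affected.

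**What to change.** Change the programming note so that Tables 6.13-6.15 show every pre-agreed probeset whatever its adjusted p-value, with ordinary 95% intervals where a model is fitted. Tables 6.13 and 6.15 also omit rows with an adjusted mean fold change between -1 and 1; that exclusion should not apply to the pre-agreed block, or it would bring the gap back.

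List FDR-selected probesets in a separate block labelled as selected on these data and descriptive, without a second p-value presented as confirmation. State the adjusted p-value cut-off and the model it comes from.

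Selection-adjusted intervals are optional. The false-coverage-rate level is 1 - 0.05 x R/m, with R selected out of m tested. With m = 53,617 this is about 99.998% for R = 24 and 99.97% for R = 333. The intervals become about 2.4 and 2.0 times wider, the level depends on the data, and the skewness remains.

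The cost is an edited note and more table rows, some showing no effect. No new data or model is needed.

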12.10.12. Pharmacodynamic and/or Biomarker Figures

Pharmacodynamic and or Biomarker: Figures					
No.	Population	IDSL / Example Shell	Title	Programming Notes	Deliverable [Priority]
Exploratory Biomarkers					
6.1.	Safety	EFF_F1	Individual Subject Profiles for Biopsy Tissue Inflammatory Biomarkers over Time (Parts A and B) by Randomised Treatment	Separate pages for each endpoint.	SAC [1]
6.2.	Safety	EFF_F3	Point Estimates and 95% CI for Percentage Change from Baseline in Biopsy Tissue Inflammatory Biomarkers over Time (Parts A and B) by Randomised Treatment		SAC [1]
Pathway and Target Engagement					
6.3.	Safety	EFF_F1	Individual Subject Profiles for TEAR1 % Target Engagement (Parts A and B) by Randomised Treatment	Separate pages sample type (Blood/Biopsy) Panel plot, line colours by treatment group, subjid as cell header	SAC [1]
6.4.	Safety	EFF_F3	Point Estimates and (95% CI) TEAR1 % Target Engagement in Blood (Parts A and B) by Randomised Treatment		SAC [1]
6.5.	Safety	EFF_F3	Point Estimates and (95% CI) TEAR1 % Target Engagement in Biopsy Tissue (Parts A and B) by Randomised Treatment		SAC [1]
6.6.	Safety	PD_F1	Scatter Plot of TEAR 1 % Target Engagement in Blood Versus TEAR1 % Target Engagement in Biopsy Tissue by Randomised Treatment		SAC [1]

Pharmacodynamic and or Biomarker: Figures					
No.	Population	IDSL / Example Shell	Title	Programming Notes	Deliverable [Priority]
6.7.	PK	PD_F1	Scatter Plot of TEAR 1 % Target Engagement Versus Proportion Achieving Mayo Endoscopy Remission Randomised Treatment	Separate pages sample type (Blood/Biopsy) X axis – PK concentration, Y axis – Efficacy Parameter	SAC2 [1]
6.8.	Safety	PD_F1	Scatter Plot of TEAR1 % Target Engagement Versus Change from Baseline in Total Mayo Score by Randomised Treatment	Separate pages for each biomarker parameter and sample type (blood/ Biopsy) X axis – Target Engagement, Y axis – Efficacy Parameter Different markers for each randomised treatment group	SAC2 [1]
6.9.	Safety	PD_F1	Scatter Plot of TEAR1 % Target Engagement Versus Change from Baseline in Partial Mayo Score by Randomised Treatment	Separate pages for each biomarker parameter and sample type (blood/ Biopsy) X axis – Target Engagement, Y axis – Efficacy Parameter Different markers for each randomised treatment group	SAC2 [1]
6.10.	Safety	PD_F1	Scatter Plot of TEAR1 % Target Engagement Versus Change from Baseline in 3-domain Mayo Score by Randomised Treatment	Separate pages for each biomarker parameter and sample type (blood/ Biopsy) X axis – Target Engagement, Y axis – Efficacy Parameter Different markers for each randomised treatment group	SAC2 [1]

Pharmacodynamic and or Biomarker: Figures					
No.	Population	IDSL / Example Shell	Title	Programming Notes	Deliverable [Priority]
6.11.	Safety	PD_F1	Scatter Plot of TEAR1 % Target Engagement Versus Change from Baseline in UCEIS Total Score by Randomised Treatment	Separate pages for each biomarker parameter and sample type (blood/ Biopsy) X axis – Target Engagement, Y axis – Efficacy Parameter Different markers for each randomised treatment group	SAC2 [1]
6.12.	Safety	PD_F1	Scatter Plot of TEAR1 % Target Engagement Versus Change from Baseline in Modified Riley Scale Score by Randomised Treatment	Separate pages for each biomarker parameter and sample type (blood/ Biopsy) X axis – Target Engagement, Y axis – Efficacy Parameter Different markers for each randomised treatment group	SAC2 [1]
6.13.	Safety	PD_F1	Scatter Plot of TEAR1 % Target Engagement Versus Change from Baseline in RHI by Randomised Treatment	Separate pages for each biomarker parameter and sample type (blood/Biopsy) X axis – Target Engagement, Y axis – Efficacy Parameter Different markers for each randomised treatment group	SAC2 [1]

Pharmacodynamic and or Biomarker: Figures					
No.	Population	IDSL / Example Shell	Title	Programming Notes	Deliverable [Priority]
6.14.	Safety	PD_F1	Scatter Plot of TEAR1 % Target Engagement Versus Change from Baseline in Geboes Index Total Score by Randomised Treatment	Separate pages for each biomarker parameter and sample type (blood/Biopsy) X axis – Target Engagement, Y axis – Efficacy Parameter Different markers for each randomised treatment group	SAC2 [1]
6.15.	Safety	PD_F1	Scatter Plot of TEAR1 % Target Engagement Versus Change from Baseline in CRP by Randomised Treatment	Separate pages for each biomarker parameter and sample type (blood/Biopsy) X axis – Target Engagement, Y axis – Efficacy Parameter Different markers for each randomised treatment group	SAC2 [1]
6.16.	Safety	PD_F1	Scatter Plot of TEAR1 % Target Engagement Versus Change from Baseline in FCP by Randomised Treatment	Separate pages for each biomarker parameter and sample type (blood/Biopsy) X axis – Target Engagement, Y axis – Efficacy Parameter Different markers for each randomised treatment group	SAC2 [1]
mRNA Expression					
6.17.	Safety	EFF_F1	Individual Subject Profiles for mRNA Expression of Inflammatory Gene Transcripts (Parts A and B) by Randomised Treatment	Separate pages for each gene and sample type (blood/Biopsy).	SAC2 [1]

Pharmacodynamic and or Biomarker: Figures					
No.	Population	IDSL / Example Shell	Title	Programming Notes	Deliverable [Priority]
6.18.	Safety	PD_F2	Adjusted Mean Intensities for mRNA Expression of Inflammatory Gene Transcripts (Parts A and B) by Randomised Treatment	Separate pages for each gene and sample type (blood/biopsy). .	SAC2 [1]
6.19.	Safety	PD_F3	Adjusted Mean (95% CI) Fold Change in mRNA Expression of Inflammatory Gene Transcripts (Parts A and B) by Randomised Treatment	Separate pages for each gene and sample type (blood/biopsy). Include band from FC -1 to 1, transparency 0.5	SAC2 [1]

12.10.13. ICH Listings

ICH: Listings					
No.	Population	IDSL / Example Shell	Title	Programming Notes	Deliverable [Priority]
Subject Disposition					
1.	All Subjects	ES7	Listing of Reasons for Screen Failure by Randomised Treatment	Journal Guidelines	IA SAC [1] SAC [1]
2.	Safety	ES2	Listing of Reasons for Study Withdrawal by Randomised Treatment	ICH E3	IA SAC [1] SAC [1]
3.	Safety	SD2	Listing of Reasons for Study Treatment Discontinuation by Randomised Treatment	ICH E3	IA SAC [1] SAC [1]1]
4.	Safety	BL1	Listing of Subjects for Whom the Treatment Blind was Broken During the Study by Randomised Treatment	ICH E3	IA SAC [1] SAC [1]
5.	Safety	TA1	Listing of Planned and Actual Treatments	IDSL	IA SAC [1] SAC [1] [1]
Protocol Deviations					
6.	Safety	DV2	Listing of Important Protocol Deviations by Randomised Treatment	ICH E3	IA SAC [1] SAC [1]
7.	Safety	IE3	Listing of Subjects with Inclusion/Exclusion Criteria Deviations by Randomised Treatment	ICH E3	IA SAC [1] SAC [1]1]
Populations Analysed					
8.	Safety	SP3	Listing of Subjects Excluded from Any Population by Randomised Treatment	ICH E3	IA SAC [1] SAC [1]

ICH: Listings					
No.	Population	IDSL / Example Shell	Title	Programming Notes	Deliverable [Priority]
Demographic and Baseline Characteristics					
9.	Safety	DM2 / DM4	Listing of Demographic Characteristics by Randomised Treatment	ICH E3	IA SAC [1] SAC [1]
10.	Safety	DM9 / DM10	Listing of Race by Randomised Treatment	ICH E3	IA SAC [1] SAC [1]

ICH: Listings					
No.	Population	IDSL / Example Shell	Title	Programming Notes	Deliverable [Priority]
11.	Safety	DM2	Listing of Ulcerative Colitis Baseline Characteristics by Randomised Treatment	
To include: Baseline Mucosal Appearance at Endoscopy Mayo Subscore, Baseline Total Mayo Score, Baseline Partial Mayo Score Baseline 3-domain Mayo Score, Baseline UCEIS Total Score, Baseline Modified Riley Scale Score Baseline FCP, Baseline FCP category, Baseline Concomitant Medications for UC (Glucocorticoids only, Immunosuppressants only, Glucocorticoids and Immunosuppressants, No Glucocorticoids or Immunosuppressants, Baseline Prednisone dose, Family History of Premature Coronary Artery Disease and History of Tobacco Use.
 
Include the footnote: Note: Glucocorticoids and Immunosuppressants were identified by review of all ingredients by clinical and medical team.
	IA SAC [1] SAC [1]
Prior, Current and Concomitant Medications					
12.	Safety	MH2	Listing of Medical Conditions by Randomised Treatment		IA SAC [1] SAC [1]

ICH: Listings					
No.	Population	IDSL / Example Shell	Title	Programming Notes	Deliverable [Priority]
13.	Safety	CP_CM3	Listing of Concomitant Medications by Randomised Treatment	IDSL	IA SAC [1] SAC [1]
Exposure and Treatment Compliance					
14.	Safety	EX3 / EX4	Listing of Exposure Data by Randomised Treatment	ICH E3	IA SAC [1] SAC [1]
15.	Safety	COMP3A/ COMP3B	Listing of Drug Accountability Data by Randomised Treatment		IA SAC [1] SAC [1]
Adverse Events					
16.	Safety	AE9CP	Listing of All Adverse Events by Period Treatment	ICH E3	IA SAC [1] SAC [1]
17.	Safety	AE7	Listing of Subject Numbers for Individual Adverse Events by Period Treatment	ICH E3	IA SAC [1] SAC [1]1]
18.	Safety	AE2	Listing of Relationship Between Adverse Event System Organ Classes, Preferred Terms, and Verbatim Text	IDSL	IA SAC [1] SAC [1]]
Serious and Other Significant Adverse Events					
19.	Safety	AE9CPa	Listing of Fatal Serious Adverse Events by Period Treatment	ICH E3	IA SAC [1] SAC [1]
20.	Safety	AE9CPa	Listing of Non-Fatal Serious Adverse Events by Period Treatment	ICH E3	IA SAC [1] SAC [1]
21.	Safety	AE14	Listing of Reasons for Considering as a Serious Adverse Event by Period Treatment	ICH E3	IA SAC [1] SAC [1]

ICH: Listings					
No.	Population	IDSL / Example Shell	Title	Programming Notes	Deliverable [Priority]
22.	Safety	AE9CP	Listing of Adverse Events Leading to Withdrawal from Study / Permanent Discontinuation of Study Treatment by Period Treatment	ICH E3	IA SAC [1] SAC [1]
23.	Safety	AE9CP	Listing of Other Significant Adverse Events by Period Treatment	ICH E3	IA SAC [1] SAC [1] [1]
24.	Safety	PSRAE1	Listing of Possible Suicidality-Related Adverse Event Data: Event and Description (Section 1- Section 2) by Period Treatment	IDSL	IA SAC [1] SAC [1]
25.	Safety	PSRAE2	Listing of Possible Suicidality-Related Adverse Event Data: Event and Description (Sections 1- Section 2) by Period Treatment	IDSL	IA SAC [1] SAC [1]1]
26.	Safety	PSRAE3	Listing of Possible Suicidality-Related Adverse Event Data: Possible Cause(s) (Section 3) by Period Treatment	IDSL	IA SAC [1] SAC [1]
27.	Safety	PSRAE4	Listing of Possible Suicidality-Related Adverse Event Data (Section 4) by Period Treatment	IDSL	IA SAC [1] SAC [1]1]
Hepatobiliary (Liver)					
28.	Safety	MH2	Listing of Medical Conditions for Subjects with Liver Stopping Events by Period Treatment	IDSL	IA SAC [1] SAC [1]]
29.	Safety	SU2	Listing of Substance Use for Subjects with Liver Stopping Events by Period Treatment	IDSL	IA SAC [1] SAC [1] [1]
All Laboratory					
30.	Safety	LB5	Listing of All Laboratory Data for Subjects with Any Value of Potential Clinical Importance by Period Treatment	ICH E3	IA SAC [1] SAC [1]

ICH: Listings					
No.	Population	IDSL / Example Shell	Title	Programming Notes	Deliverable [Priority]
31.	Safety	LB5	Listing of Laboratory Values of Potential Clinical Importance by Period Treatment		IA SAC [1] SAC [1] [1]
32.	Safety	LB14	Listing of Laboratory Data with Character Results by Period Treatment	ICH E3	IA SAC [1] SAC [1]]
33.	Safety	UR2A	Listing of Urinalysis Data for Subjects with Any Value of Potential Clinical Importance by Period Treatment	ICH E3	IA SAC [1] SAC [1]
34.	Safety	LB5	Listing of Lipids Outside of the Normal Range by Period Treatment	Lipids parameters = LDL Cholesterol, HDL Cholesterol, Total Cholesterol Triglycerides and Cholesterol/HDL ratio Include fasted status	IA SAC [1] SAC [1]
ECG					
35.	Safety	EG3*	Listing of All ECG Values for Subjects with Any Value of Potential Clinical Importance by Period Treatment (including manually corrected values)	IDSL EG3 plus extra columns for Manually Calculated QTcB and QTcF. Highlighted provided QTc value See 203168 Listing 89 for shell Include absolute PCI subjects. Footnote: H=High absolute, L= Low absolute. * Provided QTc	IA SAC [1] SAC [1]

ICH: Listings					
No.	Population	IDSL / Example Shell	Title	Programming Notes	Deliverable [Priority]
36.	Safety	EG3*	Listing of All ECG Changes for Subjects with a Value of Potential Clinical Importance by Period Treatment (including manually corrected values)	
Include change from baseline or change from screening PCI subjects.
 
IDSL EG3 plus extra columns for Manually Calculated QTcB and QTcF. Highlighted provided QTc value
 
Footnote: H=High change from baseline value, L= Low change from baseline value
 
* Provided QTc
	IA SAC [1] SAC [1]
37.	Safety	EG3	Listing of ECG Values of Potential Clinical Importance by Period Treatment (including manually corrected values)	
"Include absolute PCIs.
 
IDSL EG3 plus extra columns for Manually Calculated QTcB and QTcF. Highlighted provided QTc value
 
Footnote: H=High absolute, L= Low absolute."
 
* Provided QTc
	IA SAC [1] SAC [1]]

ICH: Listings					
No.	Population	IDSL / Example Shell	Title	Programming Notes	Deliverable [Priority]
38.	Safety	EG3	Listing of ECG Changes of Potential Clinical Importance by Period Treatment (including manually corrected values)	"Include change from baseline PCIs. IDSL EG3 plus extra columns for Manually Calculated QTcB and QTcF. Highlighted provided QTc value Footnote: H=High change, L= Low change."	IA SAC [1] SAC [1]
39.	Safety	EG5	Listing of All ECG Findings for Subjects with an Abnormal ECG Finding by Period Treatment	IDSL	IA SAC [1] SAC [1]
40.	Safety	EG5	Listing of Abnormal ECG Findings by Period Treatment	IDSL	IA SAC [1] SAC [1]
Vital Signs					
41.	Safety	VS4 / VS5	Listing of All Vital Signs Data for Subjects with Any Value of Potential Clinical Importance by Period Treatment	IDSL	IA SAC [1] SAC [1]
42.	Safety	VS4 / VS5	Listing of Vital Signs of Potential Clinical Importance by Period Treatment	IDSL	IA SAC [1] SAC [1]

